6.4.2.4 Hybrid Imputation

Hybrid imputation will be conducted to adjust for the effect of missing data due to the COVID-19 pandemic on the clinical trial. Missing data due to the COVID-19 pandemic includes: 1) data collected during drug interruption due to COVID-19 while a patient is considered off-drug; or 2) data which were not collected due to the COVID-19 pandemic (that is, missing visit data, in part or in whole). For the selected binary and continuous endpoints (see [Table JAIA.6.6](#)), multiple imputation (MI) will be used for imputing data that is missing due to COVID-19 in the PPCV datapoint sets (see [Table JAIA.6.6](#), PPCV definition), whereas other missing data not due to COVID-19 will be imputed by NRI for the binary endpoints and by MMRM for the continuous endpoints.

This hybrid imputation procedure addresses the hybrid estimand assuming that the effects of treatments would be the same as the PP analysis, had patients not experienced any intercurrent

event related to COVID-19 (see Section 6.4.2). The algorithm for hybrid imputation on binary and continuous endpoints (see [Table JAIA.6.4](#)) is as follows:

1. Identify all missing data, either due to COVID-19 or otherwise. Note: data following ICEs described in Section 6.4.2, will be set to missing prior to Step 2. Any data after prohibited medication or treatment/study discontinuation due to non-COVID-19 reasons will be all considered as missing due to non-COVID-19 reasons.
2. Implement the MI via PROC MI FCS REG or PROC MI FCS LOGISTIC to impute all continuous or binary missing data, respectively with treatment arm and stratified variables as covariates and generate m imputed complete data sets.
3. For each of these m imputed complete data sets from Step 2, the imputed data for missing not due to COVID-19 (as in Step 1) will be set to missing and the imputation method specified in [Table JAIA.6.6](#) will be implemented. For all other data including imputed or observed will be used for the analysis or to derive the binary outcomes.
4. Single estimates will be combined using Rubin's rules (Rubin 1987) via PROC MIANALYZE.

The number of imputed data sets will be $m=25$ and a 6-digit initial seed value prespecified for each analysis as 123456.

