For the composite binary endpoints such as SRI-4, BICLA and Lupus Low Disease Activity State (LLDAS) (see [Table JAIA.6.4](#)), the hybrid imputation algorithm will be applied on each binary component first. For each binary component, multiple imputation may be applied on the continuous variable and then dichotomized if needed.

For the corticosteroid sparing endpoint in the PPCV datapoint set, mLOCF will be conducted to handle the missing data for corticosteroid daily dose due to COVID-19 whereas missing data due to other reasons will be handled by NRI. The algorithm for hybrid imputation on Corticosteroid Sparing is as follows:

[figure not shown]
1. Identify all missing data, either due to COVID-19 or otherwise. Note: data following ICEs described in Section 6.4.2, will be set to missing prior to Step 2.
2. Implement the mLOCF to impute the missing data due to COVID-19.
3. The missing data not due to COVID-19 (as in Step 1) will be set to missing and the NRI method will be implemented. For all other data including imputed or observed will be used to derive the binary outcomes.

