6.10 Efficacy Analyses

6.10.1 General Considerations

Table JAIA.6.4 includes the description, derivation and definition of missingness for efficacy and health outcomes measures and endpoints.

Table JAIA.6.5 summarizes the data to be included/excluded in each analysis specified in Table JAIA.6.6.

Table JAIA.6.6 includes the description of the analysis method, population and primary time point(s) of analysis for efficacy and health outcomes measures. Assessments collected at multiple visits will be analyzed at each visit, in addition to the primary time point. Details of each analysis will follow the general principles described under Analysis Methods in Section 6.4.

Table JAIA.6.4. Description and Derivation of Efficacy/Health Outcomes Measures and Endpoints

Measure	Description	Variable	Derivation/Comment	Definition of Missing
SRI-4	SRI-4 is a composite index to measure overall improvement in disease activity (SLEDAI-2K) while ensuring there is no worsening in other organ systems (BILAG and PGA)	SLE Responder Index 4	
 • A decrease in SLEDAI-2K ≥ 4 (from baseline), and • No new BILAG A and no more than 1 new BILAG B disease activity score / organ domain (both compared with baseline), and • No worsening in PGA (defined as an increase of 0.3 points [10 mm] from baseline). 	Missing if any component (SLEDAI, BILAG or PGA) remains missing after each instrument level imputation rule is applied.
SLEDAI-2K	The SLEDAI-2K is a global disease activity instrument that focuses on high-impact disease manifestations across 9 organ domains: constitutional, mucocutaneous, musculoskeletal, vascular, cardiorespiratory, central nervous system, immunologic, renal, and hematologic.	SLEDAI-2K Total Score	Calculated by summing the weighted organ manifestation. For Renal domain, when the urinary casts, hematuria and pyuria items are “not done” or “not accessed”, they will be coded as “not present”.	If any or all item scores are missing (not done or not assessed), but the visit occurred, data for that item can be carried forward if obtained within previous 36 days of visit.
		Individual Organ Domain Improvement Defined by SLEDAI-2K	Patients with SLEDAI-2K score >0 within the organ domain at baseline, and able to decrease SLEDAI-2K (from baseline) within each organ domain score, separately.	Missing if any SLEDAI-2K item for that organ domain remains missing after instrument level imputation rules are applied

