		Individual Organ Domain Worsening Defined by SLEDAI-2K	Among patients with at least one SLEDAI-2K item $=0$ in the organ domain score at baseline and able to increase SLEDAI-2K (from baseline) within each organ domain score, separately.	Missing if any SLEDAI-2K item for that organ domain remains missing after instrument level imputation rules are applied.
		No worsening from baseline in SLEDAI-2K	No increment from baseline of >0 points in SLEDAI-2K	Missing if any SLEDAI-2K item for that organ domain remains missing after instrument level imputation rules are applied.

Description and Derivation of Efficacy/Health Outcomes Measures and Endpoints

Measure	Description	Variable	Derivation/Comment	Definition of Missing
BILAG-2004	BILAG-2004 assesses 97 clinical signs, symptoms and laboratory parameters across nine organ system domains: constitutional, mucocutaneous, neuropsychiatric, musculoskeletal, cardiorespiratory, gastrointestinal, ophthalmic, renal and hematological	BILAG	A, B, C, D, or E score will be used in analyses for each of the 9 individual organ systems.	Within each organ domain (except renal and hematological), any missing data will be assumed to be 'Not present' if there is at least 1 non-missing item in that organ. If all items in one organ domain are completely missing but the visit occurred, then the letter score of that organ from the previous visit will be pulled forward, provided data were obtained within 36 days of visit; otherwise missing except when the letter score from the last non-missing visit is E, then E score will be pulled forward. For renal and hematological domain, if any item is missing but there is at least 1 non-missing item in the organ, the missing data will be assumed to be "No". If any vital/lab item with "Yes" but vital and lab value is missing, then vital/lab values will be pulled forward, provided data were obtained within 36 days of visit; otherwise missing. After the value imputation, if the A/B/C score for the organ domain still cannot be derived, then the letter score of that organ from the previous visit will be pulled forward, provided data were obtained within 36 days of visit; otherwise missing except when the letter score from the last non-missing visit is E, then E score will be pulled forward.

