		BILAG improvement	Reduction of all baseline BILAG A to B/C/D and baseline BILAG B to C/D and no BILAG worsening in other organ systems, where worsening is defined as ≥ 1 new BILAG A or ≥ 2 new BILAG B	Missing if any of 9 domains at baseline or at the visit remains missing after instrument level imputation rules are applied except when the missing is at the baseline (any one or all domains) and the value at the visit is not A or B, then the other non-missing organ domains will be used to determine the response status.

Description and Derivation of Efficacy/Health Outcomes Measures and Endpoints

Measure	Description	Variable	Derivation/Comment	Definition of Missing
		No BILAG worsening	No new BILAG A and no more than 1 new BILAG B disease activity score (both compared with baseline), where worsening is defined as ≥ 1 new BILAG A or ≥ 2 new BILAG B, both compared with the baseline. The baseline BILAG A improved to BILAG B at the visit will not be considered as the new BILAG B.	Missing if any of 9 domains at baseline or at the visit remains missing after instrument level imputation rules are applied except when the baseline (any one or all domains) is BILAG A and the value at the visit is missing, then the other non-missing organ domains will be used to determine the response status.
		Individual Organ Domain Improvement Defined by BILAG	Among patients with BILAG A or B at baseline and able to reduce the baseline BILAG A to B/C/D and BILAG B to C/D for each organ domain, separately.	Missing if baseline or value remains missing after instrument level imputation rules are applied.
		Individual Organ Domain Worsening Defined by BILAG	Among patients without BILAG A at baseline, an increment of baseline BILAG B/C/D/E to A or baseline BILAG C/D/E to B for each organ domain, separately.	Missing if baseline or value remains missing after instrument level imputation rules are applied.

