6.10.3.3.1 Tipping Point Analyses

Planned tipping point analyses will be conducted provided the associated nominal p-value is significant. An interpretation of clinical plausibility of the assumption underlying the tipping point will be provided. This analysis will be performed on SRI-4 at the Week 52 visit to assess the robustness of the primary analysis.

Based on the evaluation of baricitinib SLE Phase 2 data (Study JAHH), the adjusted odds ratios are expected to be similar to unadjusted odds ratios, and therefore the tipping point analyses will be unadjusted for covariates. In this analysis, patients who have not had a treatment failure, but are missing data at the Visit 16 (Week 52) time point, will have their response status changed from not achieving response to achieving response, in an iterative manner.

At each step of the analysis, one subject will be switched from not achieving SRI-4 response to achieving SRI-4 response and the analysis re-run. The results (statistical significance) will be presented in a grid where the x-axis and y-axis represent the number of subjects assumed to achieve SRI-4 in the placebo group and the given baricitinib treatment group, respectively. The region where the conclusion changes will be considered as the tipping point.

The grid will be divided in 3 regions, limited in the top by the expected number of subjects from the baricitinib treated arm that could have achieved SRI-4 had they had sufficient data and could have achieved SRI-4 response, and limited from the right by the number of subjects in the equivalent placebo group.

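### The BILAG missing-data rule can relabel an observed worsening as missing, and a COVID-19 gap then lets the primary analysis impute it as success

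*SAP*

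**What the plan says.** Failure on the BILAG component needs little evidence: Table JAIA.6.4 gives the criterion as "where worsening is defined as ≥ 1 new BILAG A or ≥ 2 new BILAG B, both compared with the baseline". One or two domains can settle it.

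The missing-data column for the same variable reads "Missing if any of 9 domains at baseline or at the visit remains missing after instrument level imputation rules are applied except when". For No BILAG worsening the exception is "except when the baseline (any one or all domains) is BILAG A and the value at the visit is missing"; the remaining recorded domains then decide the result. No other exception is written.

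The composite follows the same pattern. SRI-4 is "Missing if any component (SLEDAI, BILAG or PGA) remains missing after each instrument level imputation rule is applied". The SLEDAI-2K no-worsening variable, which feeds BICLA and not SRI-4, is "Missing if any SLEDAI-2K item for that organ domain remains missing after instrument level imputation rules are applied".

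Section 6.4.2.4 defines the data to be multiply imputed as those missing because of COVID-19, including "data which were not collected due to the COVID-19 pandemic (that is, missing visit data, in part or in whole". Other missing binary data go to non-responder imputation (NRI). For SRI-4, BICLA and LLDAS, "the hybrid imputation algorithm will be applied on each binary component first". Section 6.10.2 and Table JAIA.6.6 make NRI with multiple imputation (MI) on the PPCV datapoint set the primary analysis.

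The tipping-point analysis (Section 6.10.3.3.1) switches "patients who have not had a treatment failure, but are missing data at the Visit 16 (Week 52) time point" from non-response to response, one at a time.

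**The concern.** A missing label should mean that the outcome is unknown. Here it can be attached to an outcome that is known. If a new BILAG A has been recorded, nothing in a blank renal or haematological domain can undo it.

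Under pure NRI the label is harmless, because missing and failed lead to the same score. Under the hybrid approach they differ: missing because of COVID-19 means a draw from an imputation model, and some draws will be successes. That replaces an observed non-response with an imputed response in the primary analysis. No missing-data assumption justifies this, since nothing about the result is missing.

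The component is also a stand-alone secondary endpoint analysed with NRI plus MI, so the same error enters there directly.

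**Working it through.** **1. The rule applied to example patients.** Each has an observed failure on the BILAG component.

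| Patient | Observed at the visit | Missing domain(s) | Rule returns |
|---|---|---|---|
| 1 | Mucocutaneous B to A (new A) | Renal (baseline D), haematological (baseline C) | Missing |
| 2 | Constitutional E to B and cardiorespiratory E to B (two new Bs) | Renal (baseline D) | Missing |
| 3 | Mucocutaneous B to A (new A) | Constitutional (baseline A) | Failed |

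Patients 1 and 3 have the same proven failure. They are labelled differently only because of the baseline letter of a domain that cannot alter it.

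**2. When the label reaches MI.** All of these must hold:
- The gap is due to COVID-19; otherwise NRI applies.
- It survives the BILAG item rules in Table JAIA.6.4. If at least one item in a domain is recorded, missing items are taken as absent. Failing that, the earlier letter is carried forward if obtained within 36 days, and a last letter of E is carried forward regardless of age.
- SLEDAI-2K and PGA are met, or are themselves imputed as met. Imputation is by component, so an observed failure on either keeps SRI-4 failed.

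On timing, Week 48 to Week 52 is 28 days. With ±4-day windows at both ends the longest in-window gap is 28 + 4 + 4 = 36 days, so a Week 48 letter normally covers an in-window Week 52 visit. Section 5.1, however, allows Visit 16 to be delayed by up to one month for COVID-19. With Week 48 on its nominal day, a delay of more than 36 − 28 = 8 days puts it out of reach. Successive gaps have the same effect.

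**3. The plan's own figure.** Section 5.2 gives 750 patients at 1:1:1 (250 per arm), 40% against 57%, two-sided α 0.05, power above 90%. With pooled rate 0.485:

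z = [0.17·√250 − 1.96·√(2·0.485·0.515)] / √(0.40·0.60 + 0.57·0.43) = (2.688 − 1.385)/0.696 = 1.87, so power = 0.969. The stated figure is reproduced.

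**4. Illustrative size.** Let f be the share of an arm with a proven BILAG failure coded missing and sent to MI, and π the chance that such a patient is drawn as an SRI-4 responder. The SAP gives neither; both are assumptions. Correct scoring adds no responders. The text as written adds n·f·π per arm, and the apparent difference is 0.17 + f_T·π_T − f_C·π_C (T baricitinib, C placebo).

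- Lowest assumed case: 250 × 0.004 × 0.3 = 0.3 responders per arm.
- Highest assumed case: 250 × 0.04 × 0.9 = 9 responders per arm (3.6 points).
- Equal f and π in both arms: the difference stays at 17.0 points.
- f = 4% in both arms, π = 0.40 placebo and 0.57 active: 59.28 − 41.60 = 17.7 points.
- f = 4% placebo and 2% active, π = 0.9: 58.8 − 43.6 = 15.2 points (power 0.927).
- f = 2% placebo and 4% active, π = 0.9: 60.6 − 41.8 = 18.8 points.

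**5. Related variables.** BILAG improvement and SLEDAI-2K no worsening carry the same explicit any-missing rule; they affect BICLA and stand-alone endpoints. For the SLEDAI-2K total score the table gives carry-forward and then stops. If baseline is 10 and recorded items already sum to 8, a total of 6 or less is impossible because missing items can only add points; yet the text does not say how the visit is scored. The LLDAS SLEDAI-2K criterion is silent in the same way.

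**The case against.** The strongest reply is that few patients can follow this route. The item rules, the 36-day carry-forward and the unlimited carry-forward of E fill most gaps at an in-window Week 52 visit. MI touches only COVID-19 gaps, and an observed failure on another component cannot be overturned. All of this stands and limits the point to a narrow group. It does not make the rule correct for that group.

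A reader might infer four stronger things that the SAP does not support.

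- *That the written exceptions only help the patient.* They pass the decision to the other domains, which can return failure, as patient 3 shows.
- *That the bias favours baricitinib because treatment arm is in the imputation model.* That requires similar f in the arms and a higher imputed success rate on baricitinib. The relevant rate is that of the BILAG component, which the SAP does not state. If placebo patients have more proven worsenings, the error shrinks the difference.
- *That the SLEDAI-2K part of SRI-4 has the same written flaw.* The explicit any-missing-item rule belongs to the no-worsening and organ-domain variables; for the total score it is only implied.
- *That the tipping-point analysis certainly switches proven failures.* The composite missing label would admit them, and not only for COVID-19 gaps. But the section excludes treatment failures and bounds its grid by patients who could have responded. Treatment failure is not defined there, so the text is ambiguous rather than clearly permissive.

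**Conclusion.** The point holds in narrow form and should be corrected. The rule for No BILAG worsening gives a wrong label when recorded domains already prove failure, and the hybrid imputation carries that error into the primary SRI-4 analysis for COVID-19 gaps that survive carry-forward, mainly a delayed Visit 16 or successive gaps. The same explicit flaw touches BICLA and its components; for the SLEDAI-2K total score and LLDAS the text is silent rather than wrong.

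The effect is probably small. The range of 0.3 to 9 added responders per arm of 250, and differences of 15.2 to 18.8 points against a planned 17.0, rest entirely on assumed f (0.4% to 4%) and π (0.3 to 0.9). They show that the direction is open and do not estimate the bias. The case for correction rests on the logic of the rule, not on these figures.

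**What to change.** Add one rule to the missing-data column of Table JAIA.6.4, applied before any component is labelled missing: the component is failed if the non-missing data already make success impossible. Specifically:

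- No BILAG worsening: at least one new A, or at least two new Bs, in recorded domains.
- BILAG improvement: as above, or any recorded baseline A or B not reduced as the definition requires.
- SLEDAI-2K criteria: recorded items alone already exceed the threshold (baseline minus 4 for the 4-point reduction; baseline for no worsening; 4, or any recorded major-organ activity, for LLDAS).

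State also how the SLEDAI-2K total is handled when an item remains missing after carry-forward, and that any observed failed component makes SRI-4, BICLA or LLDAS a non-response. In Section 6.10.3.3.1, define treatment failure and say that patients with a proven or observed failed component cannot be switched.

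The cost is a few lines of text and derivation code, with no new data. Reported response rates may fall slightly.

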6.3 Definition of Baseline and Postbaseline Periods

For efficacy analyses (excluding daily diaries), baseline is defined as the last non-missing value prior to the first dose of study drug, unless otherwise specified. In most cases, this will be the measurement recorded at Week 0 (Visit 2).

Baseline for the safety analyses is defined as:

- The last non-missing scheduled (planned) measurement prior to the first dose of the study drug for continuous measures by-visit analyses, and
- All non-missing measurements prior to the first dose of the study drug for all other analyses.

In general, for efficacy and safety (except adverse events) analyses, when the baseline measurement is collected on the same day (where time is not collected) as the first dose date, this measurement will be used as the baseline value for data analysis.

Postbaseline measures for the safety analyses are defined as the non-missing scheduled (planned) measurements after the first dose of the study drug for continuous measures by-visit analyses and all non-missing measurements after the first dose of the study drug for all other analyses.

Postbaseline data collection begins after the first dose of study drug administration at Visit 2 (Week 0) and will continue through Visit 16 (Week 52), early study termination visit, or the follow-up visit.

The baseline value for the daily diary assessments (Worst Pain Numeric Rating Scale [NRS], Worst Joint Pain NRS, Worst Fatigue NRS, Joint Stiffness Duration, Joint Stiffness Severity NRS, and Patient Global Impression of Severity [PGI-S]) is defined as the average of the non-missing assessments in the last 7 days prior to the date of first study drug administration (expected at Week 0, Visit 2). There must be at least 4 non-missing daily measurements in the 7 days indicated. If there are less than 4 non-missing daily assessments collected prior to the date of first study drug administration, then the baseline value will be designated as missing. If there are multiple assessments collected on the same day, only the first collected record will be used.

Postbaseline values of daily diary assessments collected after first study drug administration through Visit 16, or early study termination visit, will be defined as the average of the last 7 days prior to the date of the study visit. If less than 4 non-missing daily measurements are present, the visit will be set to missing.

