6.4.2.1 Non-responder Imputation (NRI)

The non-responder imputation (NRI) method may be used when the estimand of interest uses the composite strategy (EMA 2020) for handling intercurrent events. In this strategy, patients will be considered non-responders for the NRI analysis if they do not meet the clinical response criteria or have missing clinical response data (based on each set of [Table JAIA.6.5](#)) at the analysis time point.

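### SRI-4's BILAG component is set to missing when a baseline domain is missing, even if the visit letter already rules out a new A or B

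*SAP*

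**What the plan says.** Both BILAG composite variables in SAP Section 6.10.1, Table JAIA.6.4, start from the same default: "Missing if any of 9 domains at baseline or at the visit remains missing after instrument level imputation rules are applied". Their exceptions then differ.

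- **BILAG improvement** (feeds BICLA): the default applies "except when the missing is at the baseline (any one or all domains) and the value at the visit is not A or B". In that case the other non-missing domains decide.
- **No BILAG worsening** (feeds SRI-4): the default applies "except when the baseline (any one or all domains) is BILAG A and the value at the visit is missing". Here too the other domains decide, but nothing is said about a missing baseline.

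Both rows use one threshold for worsening: at least one new A, or at least two new Bs. The No BILAG worsening row adds that a baseline A improving to B is not a new B.

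The consequence for the primary endpoint follows from three further rules:

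- SRI-4 (same table): "Missing if any component (SLEDAI, BILAG or PGA) remains missing after each instrument level imputation rule is applied".
- Section 6.4.2.1: "patients will be considered non-responders for the NRI analysis if they do not meet the clinical response criteria or have missing clinical response data".
- Section 6.4.2.4, for the hybrid method used in the primary analysis: COVID-19 gaps are multiply imputed, "whereas other missing data not due to COVID-19 will be imputed by NRI for the binary endpoints".

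**The concern.** The improvement row rests on a sound principle: if a missing value cannot change the result, use the remaining domains. The baseline-A exception in the No BILAG worsening row rests on the same principle, because a domain already at A cannot produce a new A or B. The mirror case, baseline missing and visit C, D or E, is just as determined but is left out.

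The two rows are therefore inconsistent. The improvement definition includes absence of worsening in other organ systems at the same threshold. For one patient with one missing baseline domain and a visit letter of C, D or E there, the SAP accepts that worsening can be judged for BICLA and declares it unjudgeable for SRI-4.

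A missing baseline stays missing, so the effect recurs at every visit. It reaches SRI-4 at Week 52 (primary) and Week 24 (major secondary), and the separate secondary analysis of no new BILAG A and at most one new BILAG B.

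**Working it through.** **1. Is the domain result determined?** Define, per domain, new A = visit A with baseline not A, and new B = visit B with baseline C, D or E. Run through all five possible baseline letters for each visit letter.

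| Baseline missing, visit letter | Could be a new A? | Could be a new B? | Determined? |
|---|---|---|---|
| A | yes, unless baseline was A | no | no |
| B | no | yes, unless baseline was A or B | no |
| C | no | no | yes, not worsened |
| D | no | no | yes, not worsened |
| E | no | no | yes, not worsened |

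In the other direction (visit missing, baseline known), only baseline A is determined. That is the one case the No BILAG worsening row already excepts.

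**2. What the rules do with a missing baseline domain and visit C, D or E**

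| | BILAG improvement | No BILAG worsening |
|---|---|---|
| Default | missing | missing |
| Exception met? | yes | no |
| Result | other domains decide | missing |
| Composite | BICLA's BILAG part evaluable | SRI-4 missing |
| Under NRI | decided on the data | non-responder |

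**3. The plan's power figure.** Inputs from SAP Section 5.2: about 750 patients randomized 1:1:1, so 250 per arm; placebo 40%; difference 17 points, so active 57%; two-sided alpha 0.05.

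z = [d√n − 1.96·√(2·p̄·(1−p̄))] / √(p₁(1−p₁) + p₂(1−p₂))

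= [0.17 × 15.811 − 1.96 × √(2 × 0.485 × 0.515)] / √(0.2400 + 0.2451)

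= (2.688 − 1.385) / 0.6965 = 1.870, giving power 96.9%. This agrees with the stated figure of more than 90%.

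**4. Size of the effect.** The SAP gives no share of affected patients. Let m be an assumed share, equal in all arms, whose responses are all lost to NRI. The rates become 0.40(1−m) and 0.57(1−m), and the difference 0.17(1−m).

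| m (assumed) | Patients per arm (250m) | Loss of difference (17m points) | Power |
|---|---|---|---|
| 0 | 0 | 0 | 96.9% |
| 0.5% | 1.25 | 0.09 | 96.8% |
| 1% | 2.5 | 0.17 | 96.7% |
| 2% | 5 | 0.34 | 96.4% |
| 5% | 12.5 | 0.85 | 95.4% |

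At 0.5–2% the placebo rate loses 0.2–0.8 points (0.40 × m) and the active rate 0.3–1.1 points (0.57 × m). The quantity that matters for inference is the gap between these losses, 0.09–0.34 points.

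This is an upper bound on what the repair recovers. Patients whose missing-baseline domain is A or B at the visit stay missing under it.

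**The case against.** Several points on the other side have force.

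- **Reach.** A reader might infer that every such patient is an SRI-4 non-responder in every analysis. The SAP does not support that. In the PPCV primary analysis the hybrid method is applied to each component and multiply imputes gaps due to COVID-19. This limit stands.
- **Frequency.** For efficacy, "baseline is defined as the last non-missing value prior to the first dose of study drug, unless otherwise specified". In addition, a partly missing domain is filled as not present (or as No for renal and hematological items), letters within 36 days are pulled forward, and an E is carried forward without that limit. Few domains should remain missing at baseline. This stands.
- **Bias.** Baseline precedes treatment, so the loss is non-differential in expectation. The SAP gives no ground for reading it as favouring either arm.
- **Tipping-point analysis** (Section 6.10.3.3.1). It switches patients with missing Week 52 data from non-response to response. But it runs only if the nominal p-value is significant, covers Week 52 only, and tests robustness without correcting the estimate.
- **Convention.** Other rows also make a missing baseline decisive: no worsening in PGA and individual organ worsening by BILAG are missing without a baseline. Conservative handling is defensible as a general rule. It does not explain why this row makes the baseline-A deduction and omits its mirror image, or why the neighbouring row differs.

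A reader might also infer that the improvement row hands out BICLA responses by default when baseline domains are missing. That does not hold as a fault. With C or D at the visit, a domain meets the improvement criterion whatever its baseline letter. E is not among the listed target letters, but a patient with complete baseline data and no A or B likewise has nothing to reduce. With all nine baseline domains missing, the row points to other non-missing domains when there are none, so it states no default response. BICLA is also outside the multiplicity-controlled set.

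**Conclusion.** The inconsistency is real and follows from the SAP's text alone. As written, the No BILAG worsening row discards a domain result that is logically settled, and the SRI-4 and NRI rules then record failure. It is a minor point. At an assumed 0.5–2% of patients, equal across arms, the treatment difference shrinks by about 0.1–0.3 points and power falls from 96.9% to 96.8–96.4%. The asymmetry is certain; the size rests wholly on the assumed share. The documents do not support any claim that the primary conclusion is at risk or that the comparison is biased.

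**What to change.** Add one sentence to the Definition of Missing for No BILAG worsening in Table JAIA.6.4: when a baseline domain is missing and that domain's letter at the visit is not A or B, the other non-missing domains determine the status. Keep the existing baseline-A exception, and leave the BILAG improvement and BICLA rows unchanged.

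The cost is one sentence and a small change to the derivation program. It does not alter the definition of response, and a missing-baseline domain scored A or B at the visit would still leave the component missing. A count of patients with any baseline BILAG domain still missing after the fill rules would show whether the case arises at all.
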